18.1. DERIVATIONS

For each day where a blood sample for PK concentration is planned to be collected, the time of the two administrations of study drug taken on a day will be compared with the time of the blood sample for PK concentration collected on that day as follows in order to derive the timepoint categories specified in Section 18:

CCI				
PPD			Version Number:	Amendment 1, v1.0
CCI			Version Date:	23Apr2021

CCI [Redacted]

- Time post morning administration of study drug (hours) = {[Time (hours & minutes) of collection of the blood sample for PK concentration – Time (hours & minutes) of the morning administration of the study drug] + 1} / 60 minute if time of collection of the blood sample for PK concentration is before the time of the evening administration of the study drug;
- Time post evening administration of study drug (hours) = {[Time (hours & minutes) of collection of the blood sample for PK concentration – Time (hours & minutes) of the evening the administration of study drug] + 1} / 60 minute if time of collection of the blood sample for PK concentration is on or after the time of the evening administration of the study drug but before the time of the morning administration of study drug of the next day.

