## 1.2 Schedule of Activities

	Screening	Baseline				
Day (± Window)	Day -1 or Day 1	Day 1	Daily Until Hospital Discharge (or Daily Until Day 29 While in Hospital)	Day 15 a (±2 days)	Day 29 a (±3 days)	Day 60 a (±4 days) (End of Study)
ELIGIBILITY						
Informed consent	X					
Demographics	X					
Relevant medical history b	X					
Review of SARS-CoV-2 diagnostic tests (obtained during the previous 72 hours, if available)	X					
SARS-CoV-2 diagnostic test c	X					
Inclusion and exclusion criteria	X	X				
12-lead electrocardiogram	X					
STUDY INTERVENTION						
Randomization		X				
Administration of study treatment BID		Daily from Day 1 to Day 14 or until hospital discharge, whichever occurs first				
Treatment with SoC		SoC will be based on the practices of the study center				
STUDY PROCEDURES						
Physical examination (including height and weight) d	X					
Vital signs, including body temperature, pulse rate, blood pressure, respiratory rate, SpO 2 , FiO 2 e		X f	X	X g	X g	
CCI						

	Screening	Baseline				
Day (± Window)	Day -1 or Day 1	Day 1	Daily Until Hospital Discharge (or Daily Until Day 29 While in Hospital)	Day 15 a (±2 days)	Day 29 a (±3 days)	Day 60 a (±4 days) (End of Study)
Ordinal scale		X f	X	X	X	X
Clinical assessments b		X f	X	X	X	X i
Assessment of floor status (ICU yes/no)		X	X g	X g	X g	
Assessment of rehospitalization for discharged patients j				X	X	X
Concomitant medication review (including use of vasopressors)	X	X f	X	X	X	X
Adverse event evaluation	X	X	X	X	X	X
SAFETY LABORATORY						
Clinical safety laboratory assessments	X k,l	X f,m,n	Days 3 o , 8 m , 22 m , and at discharge m,p All other days while in hospital q	X m,r	X m	
Pregnancy test for females of childbearing potential	X k					
RESEARCH LABORATORY						
Blood for pharmacokinetic assessment			Day 8	X		
CCI						

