### **4.1 Pharmacokinetic Assessments**

Blood will be collected on Days 8 and 15 for assessment of apremilast concentrations. The date and time of the pharmacokinetic sample collection will be documented on the electronic case report form (eCRF).

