## **5.0 SUB-PROTOCOL STUDY TREATMENT**

### **5.1 Treatment Plan**

Patients will receive BID either apremilast 30 mg or placebo in a double-blind manner plus SoC for 14 days or until hospital discharge, death, or discontinuation of investigational product, whichever occurs first.

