### **5.2 Study Drug Administration**

The tablet formulation of apremilast or placebo will be provided in a double-blind manner in bottles throughout the entire study.

Double-blind treatment (apremilast or placebo) will be taken orally BID, with doses approximately 12 hours apart, without restriction of food or drink.

CCI [REDACTED]

The quantity of tablets, type of administration (intact or disintegrated tablets), date/time of each dose, and box number of study treatment are to be recorded on the patient's eCRF.

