14. EXPOSURE TO STUDY DRUG

Patients randomized to sub-protocol COV-01-004

Patients randomized to the apremilast plus SoC or placebo plus SoC treatment groups of COV-01-004 sub-protocol will receive either an apremilast 30 mg or matching placebo tablet, as applicable, twice daily (BID) in a double-blind manner for 14 days or until hospital discharge, death, or discontinuation of study drug, whichever occurs first, in addition to SoC.

Reason for dose modification of study drug (i.e., dose increased, dose reduced, drug interrupted, drug withdrawal, and unknown) will be captured on the *Exposure* page of the electronic Case Report Form (eCRF).

Patients included in the control arm of COV-01-004 sub-protocol who were randomized to the placebo plus SoC group of a sub-protocol other than COV-01-004

It is to be noted that the planned duration of exposure to a study drug, planned frequency of administration of the study drug, and planned route of administration of the study drug will vary from one sub-protocol to the other, but similar information as for COV-01-004 sub-protocol will be captured on the *Exposure* page of the eCRF of these other sub-protocols.

[figure not shown]
CCI [Redacted]

PPD [Redacted]

Version Number: Amendment 1, v1.0
Version Date: 23Apr2021

CCI [Redacted]

[figure not shown]
[Redacted]

Exposure to study drug

The exposure to study drug will be summarized by treatment arm (breaking down the placebo plus SoC arm by sub-protocol) based on the safety analysis set as follows:

- Duration of exposure:
 - Duration of exposure (days) as a continuous variable;
 - Duration of exposure (days) as a categorical variable: 1 to 3, > 3 to 7, > 7 to 14, and > 14;
 - Total number of doses received as a continuous variable, where the total number of doses received is defined as the total number of doses received by each patient, not the total number of doses received across all patients.
- Average dose (mg/day) only for patients randomized to sub-protocol COV-01-004;
- Dose modifications:
 - Number and percentage of patients with at least one dose reduction;
 - Number and percentage of patients with a dose reduction by reason for dose reductions:
 - Adverse events;
 - Due to creatinine clearance < 30 mL/min*;
 - Due to renal replacement therapy*;
 - Other.
 - Total number of dose reductions as a continuous variable, where the total number of dose reductions defined similarly to the total number of doses received;

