18. PHARMACOKINETICS

PK concentrations of apremilast will be summarized and listed by visit and timepoints based on the PK analysis set. In addition to the descriptive statistics mentioned in Master COV-01 SAP Appendix 2, the coefficient of variation (CV%), geometric mean, geometric standard deviation (SD), and geometric CV% will also be provided for the PK concentrations. Concentrations that are below the limit of quantification (BLQ) will be treated as a numeric value of zero.

PK concentrations of apremilast will be summarized for the following time categories:

- 0 - < 3 hours post morning administration of study drug;
- 3 - <6 hours post morning administration of study drug;
- 6 - < 9 hours post morning administration of study drug;
- 9 - <12 hours post morning administration of study drug
- 0 - < 3 hours post evening administration of study drug;
- 3 - <6 hours post evening administration of study drug;
- 6 - < 9 hours post evening administration of study drug;
- 9 - <12 hours post evening administration of study drug.

Scatter plots of plasma concentrations against the time since last dose, in hours, will be provided for each day and each dose of study drug (i.e., Day 8 post morning administration of study drug, Day 8 post evening administration of study drug, Day 15 post morning administration of study drug, and Day 15 post evening administration of study drug).

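### Apremilast PK samples are timed from same-day doses in categories that stop below 12 hours, although the Day 15 sample is scheduled after dosing ends on Day 14

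*SAP*

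**What the plan says.** **Dosing.** The COV-01-004 sub-protocol's Schedule of Activities (1.2) sets twice-daily dosing "Daily from Day 1 to Day 14 or until hospital discharge, whichever occurs first". Section 5.1 gives the same limit: "for 14 days or until hospital discharge, death, or discontinuation of investigational product, whichever occurs first". The COV-01-004 SAP repeats it in Section 14: "twice daily (BID) in a double-blind manner for 14 days or until hospital discharge, death, or discontinuation of study drug, whichever occurs first". Doses are taken "with doses approximately 12 hours apart" (sub-protocol 5.2).

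**Sampling.** Sub-protocol 4.1: "Blood will be collected on Days 8 and 15 for assessment of apremilast concentrations". No clock time relative to a dose is set. The Day 15 column of the Schedule carries a window of ±2 days.

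**Classification.** SAP Section 18 has eight categories, four after the morning dose and four after the evening dose, each three hours wide and the last ending below 12 hours. It plans scatter plots on a time-since-last-dose axis in four panels. Two are "Day 15 post morning administration of study drug, and Day 15 post evening administration of study drug". It also lists all concentrations.

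**Derivation.** SAP 18.1 opens with a same-day comparison: "the time of the two administrations of study drug taken on a day will be compared with the time of the blood sample", that sample being the one collected on the same day. Two rules follow:
- Morning: applies when the sample precedes the evening dose.
- Evening: applies from the evening dose until the next day's morning dose.

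Both formulas subtract clock times in hours and minutes, add one minute and divide by 60. Neither uses a date.

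**The concern.** The derivation needs a dose on the sampling day, and the Day 15 panels are named after two such doses. On the written schedule neither dose exists. The categories assume that every sample falls within one 12-hour dosing interval, which does not hold once dosing has stopped. There is also no clean rule for a sample drawn before the morning dose.

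At stake is whether the apremilast concentration summaries and plots can be produced as specified. If not, the programmer has to invent a timing rule once the data exist. No efficacy result or error rate depends on it.

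**Working it through.** The plan states no figure to reproduce. The check applies the written rule to the written schedule. The documents give no clock times, so these are assumptions: doses at 06/18, 08/20, 09/21 or 10/22 h, and sampling spread evenly over 00–24, 06–18 or 07–12 h.

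**1. The window.** Day 15 ± 2 is Days 13 to 17. Dosing ends on Day 14, so 2 of the 5 days (13, 14) have doses and 3 of 5 (15, 16, 17) have none.

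**2. A sample on Day 15, rule as written.** There is no morning or evening dose time to subtract, so neither formula can be evaluated. Share placed: 0%, whatever the clock times.

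**3. A sample on Day 15, allowing the Day 14 evening dose.** Time = (minutes since dose + 1)/60. With a dose at 20:00 on Day 14:
- Sample at 07:30: (690 + 1)/60 = 11.5 h, which fits the last evening category.
- Sample at 08:00: (720 + 1)/60 = 12.02 h, no category.
- Sample at 10:00: (840 + 1)/60 = 14.0 h, no category.

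Sampling over 06–18 h then places about 2 of 12 hours, or 17%. Across the scenarios the share runs from 0% (06/18 dosing, sampling from 06:00 or later) to 60% (10/22 dosing, sampling 07–12 h: 3 of 5 hours). Samples on Days 16 and 17 are all beyond 12 hours. The evening rule is also left open-ended, because it closes at a next-morning dose that does not exist on Day 15.

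**4. The whole window, if sampling were uniform over Days 13 to 17 (an assumption).**
- Rule as written: on a day with doses, 40% to 100% of samples are placed. Over the window that is 2/5 × 40% = 16% to 2/5 × 100% = 40%.
- Using the last actual dose with the present categories: (2 × 100% + 0%)/5 = 40% to (2 × 100% + 60%)/5 = 52%.
- If every sample were drawn after a dose on Day 13 or 14, all would be placed.

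**5. A Day 8 sample before the morning dose.** Take 07:30, with doses at 08:00 and 20:00.
- The morning rule applies, because the sample precedes the evening dose: (−30 + 1)/60 = −0.48 h, no category.
- The evening formula on clock times alone: (−750 + 1)/60 = −12.48 h.
- With dates, from 20:00 on Day 7: (690 + 1)/60 = 11.5 h, which fits 9 to below 12 hours after the evening dose.

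**6. After the change.** Timing from the last actual dose places 100% of Day 8 samples on this schedule, up from 40% to 100%. For samples on Day 15 itself it gives only 0% to 60% until a category of 12 hours or more is added. With that category, every sample that follows a recorded dose has a place.

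**The case against.** Several points on the other side stand.

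- **Overnight clause.** The evening rule runs to the next day's morning dose, so a link from a pre-morning sample to the previous evening's dose was probably intended. A reader might infer that troughs are simply left out. The documents do not support that: the lead-in and the rule conflict, and the formula lacks the dates needed to carry out the overnight link.
- **Most Day 15 samples.** A reader might infer that most cannot be placed. The documents do not say how sampling spreads over the window. If sites sampled mainly on Days 13 and 14, most could be placed.
- **Day 8 only, or half the data.** Neither follows. Day 13 and 14 samples after a dose contribute, and one of two sampling visits is not half the samples. Patients discharged before Day 15 have that visit by telemedicine (Schedule, footnote a), and the Master SAP (7.1) assumes median recovery at 11 and 15 days. The affected share of concentrations is unknown.
- **Axis and listings.** Section 18 already plots against time since last dose and lists all concentrations. The demonstrated fault on Day 15 is that samples go unplaced, not that they are misclassified.
- **Importance.** The Master Protocol (8.6) says PK is not a primary or secondary objective.

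One further argument is that 14 days could mean 28 doses starting on the evening of Day 1, which would allow a Day 15 morning dose. The Schedule's Day 1 to Day 14 wording speaks against it, and a Day 15 evening dose would still not exist.

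None of this removes the mismatch. The panels and the same-day rule still refer to doses outside the schedule, and no category covers 12 hours or more.

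**Conclusion.** The point holds, and it is minor. As written, the rule cannot time a sample drawn on Days 15 to 17. Using the Day 14 evening dose leaves samples at 12 hours or later without a category. It also gives a pre-dose sample a negative time under one rule and conflicting instructions under the other. Two of the four planned panels are defined by doses that are not scheduled.

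The conclusion for Days 15 to 17 rests only on the dosing and sampling schedule. The percentages rest on assumed clock times and, for the whole window, on uniform sampling, so they show a range and are not a forecast. Only descriptive PK summaries and plots are affected. Efficacy and type I error are untouched.

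**What to change.** In COV-01-004 SAP 18 and 18.1:

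1. Define time since last dose as the sample date-time minus the date-time of the most recent actual dose on any day, and drop the same-day lead-in.
2. Add a category of 12 hours or more.
3. Replace the Day 15 morning and evening panels with one Day 15 plot on the existing time-since-last-dose axis.

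The cost is a short SAP edit and a small programming change. Dose date-times (sub-protocol 5.2) and sample date-times (4.1) are already recorded, so no new data are needed. The dosing and PK passages should be reconciled in the same edit. No change to dosing is proposed.

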19. PHARMACODYNAMICS

CCI [Redacted]

1. INTRODUCTION

This sub-protocol statistical analysis plan (SAP) describes the rules and conventions to be used in the presentation and analysis of data specific to COV-01-005 sub-protocol of Master Protocol COV-01. It describes the specific data to be summarized and analyzed, including specifics of the statistical analyses to be performed.

This sub-protocol SAP is based on sub-protocol version 1.2, dated 03-Nov-2020.

For the rules and conventions to be used in the presentation and analysis of data common across all sub-protocols, refer to the Master COV-01 SAP.

CCI [Redacted]

2. STUDY OBJECTIVES

The study objectives are described in the Master COV-01 SAP.

3. STUDY DESIGN

3.1. GENERAL DESCRIPTION

The general description is available in the Master COV-01 SAP.

3.2. SCHEDULE OF ACTIVITIES

Schedule of activities can be found in Section 1.2 of COV-01-005 sub-protocol.

3.3. CHANGES TO ANALYSIS FROM MASTER PROTOCOL COV-01 AND SUB-PROTOCOL COV-01-005

Enrollment into sub-protocol COV-01-005 was prematurely terminated by the Sponsor on 07-Jun-2021. In conformance with the Food and Drug Administration (FDA) Guidance for Submission of Abbreviated Report and Synopsis in Support of Marketing Application, an abbreviated Clinical Study Report (CSR) will be written for this

CCI [Redacted]
PPD [Redacted] Version Number: Amendment 2, v1.0
Version Date: 28-Jul-2021

CCI [Redacted]
[Redacted]
[Redacted]

CCI [Redacted]

sub-protocol. As such, not all analyses initially planned in the Master Protocol COV-01 and Sub-protocol COV-01-005 will be performed for this sub-protocol (refer to Section CCI [Redacted] for more details concerning the analyses to be performed for this sub-protocol).

4. PLANNED ANALYSES

The analyses initially planned to be performed are listed and described in the Master COV-01 SAP. It is to be noted that enrollment into sub-protocol COV-01-005 was terminated early by the Sponsor on 07-Jun-2021 before the trigger for the two Interim Analyses (IAs) for futility and Primary Analysis have been reached (refer to Master SAP Sections 4.2 and 4.3, respectively). Hence, these analyses will not be performed for this sub-protocol and the only analysis that will be performed, in addition to the monthly IDMC Safety analyses, is the final analysis (refer to Section 4.4).

4.1. IDMC SAFETY ANALYSES

Details are provided in the Master COV-01 SAP.

4.2. INTERIM ANALYSES

No IAs will be performed for this sub-protocol (refer to Section 4).

4.3. PRIMARY ANALYSIS

No primary analysis will be performed for this sub-protocol (refer to Section 4).

4.4. FINAL ANALYSIS

The final analysis for this sub-protocol will take place after:

- All patients to be included in this sub-protocol final analysis who were ongoing at the time Sponsor terminated early this sub-protocol completed the study (Day 60 visit) or discontinued early from the study, whichever occurs first.

CCI [Redacted]

- Sponsor Authorization of this SAP.
- Final database lock of the database including data from screen failed patients.
- Final database lock of the database of each sub-protocol contributing to the control arm of this sub-protocol (refer to Section 4.5).
- Final database lock of the database of this sub-protocol.

All planned analyses identified in this sub-protocol SAP will be performed by CCI Biostatistics at the time of the final analysis of this sub-protocol.

4.5. SELECTION OF THE CONTROL ARM FOR AN ANALYSIS

4.5.1. IDMC SAFETY ANALYSES

Details are provided in Master SAP Section 4.5.

4.5.2. FINAL ANALYSIS

For final analysis of this sub-protocol, the control arm (also referred to as shared placebo plus standard of care (SoC) arm) will include all patients randomized to the placebo arm of any sub-protocol at a site at which:

- This sub-protocol was opened for enrollment.
- At least one patient was randomized to either this sub-protocol active (zilucoplan plus SoC) or placebo (placebo to zilucoplan plus SoC) arms.

That is, patients that satisfy these criteria will be included in the control arm of this sub-protocol regardless of 1) the timing of patient’s randomization into a sub-protocol (i.e., regardless of if patient was randomized before or after this sub-protocol was opened for enrollment at the site) and 2) patient’s eligibility to this sub-protocol specific inclusion/ exclusion criteria.

The purpose of this change from the Master SAP control arm definition (Master SAP Section 4.5) is to minimize the randomization imbalance issue noted by the CCI Unblinded Biostatistician and IDMC members at the time of CCI [Redacted] At the time this sub-protocol SAP was finalized, the randomization imbalance was estimated to be approximately 7:1

CCI [Redacted]	[Redacted]	Version Number:	Amendment 2, v1.0
PPD [Redacted]	[Redacted]	Version Date:	28-Jul-2021
CCI [Redacted]	[Redacted]		
[Redacted]	[Redacted]		

CCI [Redacted]

between this sub-protocol active and control arms, should the original control arm definition would have been retained for the final analysis of this sub-protocol.

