4.5. SELECTION OF THE CONTROL ARM FOR AN ANALYSIS

The subset of the placebo plus SoC group, regardless of which sub-protocol the placebo patient belongs, enrolled concurrently to an active agent with matching inclusion/exclusion criteria will serve as the control arm for the analysis of a candidate agent. An exception to this definition is that if a sub-protocol X is not open at a site for screening, the concurrent placebo from other active sub-protocol(s) at that site will not be eligible for inclusion in the control arm for sub-protocol X. This is because patient’s eligibility for sub-protocol X cannot be determined without sub-protocol consent and obtaining consent for a sub-protocol is not possible until that sub-protocol is opened at a site for screening. It is to be noted that a patient randomized to the placebo arm of sub-protocol X taking the candidate agent of sub-protocol Y for another approved indication (based on data collected on the *Concomitant Medications* page of the eCRF) at the time of randomization will not be eligible for the control arm of the sub-protocol Y.

For each sub-protocol and each site, ‘concurrently’ is defined as the period starting on the date the site was opened

CCI [Redacted]	[Redacted]	Version Number:	Amendment 1, v1.0
PPD [Redacted]	[Redacted]	Version Date:	23Apr2021
CCI [Redacted]	[Redacted]	[Redacted]	[Redacted]
[Redacted]	[Redacted]	[Redacted]	[Redacted]
[Redacted]	[Redacted]	[Redacted]	[Redacted]

for screening for the sub-protocol and ending on the date of the last patient randomized into that sub-protocol for an interim, primary, and final analyses. For IDMC safety analyses, the date of the data cut-off will be used in lieu of the date of the last patient randomized into the sub-protocol.

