4.5.2. FINAL ANALYSIS

For final analysis of this sub-protocol, the control arm (also referred to as shared placebo + SoC arm) will include all patients randomized to the placebo arm of any sub-protocol before this sub-protocol was early terminated (refer to section 3.3) at a site at which:

- This sub-protocol was opened for enrollment.
- At least one patient was randomized to either this sub-protocol active (Lanadelumab- intra-venous [IV] + SoC) or placebo (placebo to Lanadelumab-IV + SoC) arms.

That is, patients that satisfy these criteria will be included in the control arm of this sub-protocol regardless of 1) whether patients was randomized before this sub-protocol was opened for enrollment at the site (that is, patients randomized after enrollment into COV-01-001 sub-protocol was early terminated will be excluded from the control

arm of this sub-protocol) and 2) patient’s eligibility to this sub-protocol specific inclusion/ exclusion criteria.

The purpose of this change from the Master SAP control arm definition (Master SAP Section 4.5) is to minimize the randomization imbalance issue noted by the CCI Unblinded Biostatistician and IDMC members at the time of CCI. At the time this sub-protocol SAP was finalized, the randomization imbalance was estimated to be approximately 7:1 between this sub-protocol active and control arms, should the original control arm definition would have been retained for the final analysis of this sub-protocol.

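### The redefined COV-01-005 control has no closing date, so placebo patients randomized after zilucoplan enrolment stopped on 07-Jun-2021 could enter it

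*SAP*

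**What the plan says.** COV-01-005 SAP 4.5.2 replaces the Master SAP control for the final analysis. The new control "will include all patients randomized to the placebo arm of any sub-protocol at a site at which" two conditions hold: COV-01-005 was opened for enrolment there, and at least one patient was randomized there to zilucoplan or its placebo. The section adds that neither eligibility for COV-01-005 nor timing of randomization matters, and explains the timing point as "regardless of if patient was randomized before or after this sub-protocol was opened for enrollment at the site". The stated reason is an active-to-control imbalance of about 7:1 under the Master SAP definition.

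Section 3.3 of the same SAP gives the stop date: "Enrollment into sub-protocol COV-01-005 was prematurely terminated by the Sponsor on 07-Jun-2021". That section does not list the control redefinition among the changes to planned analyses.

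COV-01-001 SAP 4.5.2 makes the corresponding change for the same stated reason, but with a limit. Its control "will include all patients randomized to the placebo arm of any sub-protocol before this sub-protocol was early terminated", and it adds that "patients randomized after enrollment into COV-01-001 sub-protocol was early terminated will be excluded from the control" arm. Its section 3.3 does list the redefinition.

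Master SAP 4.5 defines the concurrent period at each site as starting when the site opened for screening and "ending on the date of the last patient randomized into that sub-protocol". Master Protocol 4.1 likewise restricts the shared placebo group to patients randomized in the same period as the candidate agent.

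**The concern.** The COV-01-005 rule fixes which sites count but not when the pool closes. Both conditions describe a site's history, so once met they stay met after the sub-protocol has stopped. A programmer following 4.5.2 as written would keep adding placebo patients from other sub-protocols at those sites for as long as they were randomized.

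A placebo patient randomized after 07-Jun-2021 has no zilucoplan patient randomized at the same time or later. Master Protocol 4.1 says standard of care may change during the study. Differences in recovery, mortality or serious events between such patients and the zilucoplan arm could therefore reflect calendar time. Two sub-protocols of one platform would also report controls built on different rules, with no reason given for the difference.

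**Working it through.** There is no stated figure to reproduce, because this is a selection rule. The check is to set the rules side by side and apply them to one case.

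**1. Closing date in each rule**

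| Source | When the control closes |
|---|---|
| Master Protocol 4.1 | With the agent's own randomization period |
| Master SAP 4.5 | At the last patient randomized into the sub-protocol |
| COV-01-001 SAP 4.5.2 | At early termination (03-May-2021, from its section 3.3) |
| COV-01-005 SAP 4.5.2 | Not stated |

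**2. Test case.** Take a placebo patient of another sub-protocol, randomized on 08-Jun-2021 (the day after the stop) at a site that had already randomized a COV-01-005 patient.
- Master SAP 4.5: excluded, since no COV-01-005 patient can have been randomized after 07-Jun-2021.
- A rule of the COV-01-001 form, with COV-01-005's stop date: excluded.
- COV-01-005 SAP 4.5.2: included. Both site conditions are met, timing is disregarded, and the patient falls in the after-opening group, which has no upper limit.

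**3. Could such a patient exist?** The Master Protocol synopsis says enrolment continues while at least one sub-protocol is active, so it is possible. COV-01-001 had already stopped on 03-May-2021. Among the sub-protocols in these documents that leaves COV-01-004, whose enrolment after 07-Jun-2021 is not reported.

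**4. Length of the open interval.** From 07-Jun-2021 to the date of COV-01-005 SAP Amendment 2 (28-Jul-2021) is 23 + 28 = 51 days. The rule does not close at that date either.

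**5. A ceiling, not an estimate.** COV-01-005 SAP section 16 reports 108 patients randomized into the sub-protocol and expects fewer than a third of about 700 in the final analysis: 700 / 3 ≈ 233. Controls from all other sub-protocols together would then number fewer than about 233 − 108 = 125. Nothing says how many of these, if any, were randomized after 07-Jun-2021.

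**6. Outputs that use this control.** In the COV-01-005 SAP these are:
- the Kaplan-Meier curves and exact intervals for the primary endpoint (16.1.3);
- the binary and ordinal secondary summaries (16.2.3);
- the mortality summaries through Day 29 and Day 60 (16.2.5, 16.4);
- the safety tables (17), which carry over from Master SAP 17.1 the risk difference for serious treatment-emergent adverse events with its 95% Wald interval.

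The summary of adverse events of special interest (17.1.1) is restricted to patients randomized to COV-01-005 and is unaffected.

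**The case against.** The best case for leaving the text alone is that a cut-off was probably intended. COV-01-005 SAP 4.4 times the analysis by included patients "who were ongoing at the time Sponsor terminated early this sub-protocol completed the study", which fits a pool closed at termination, and the gloss on timing in 4.5.2 mentions only site opening. This makes an unstated cut-off plausible. But 4.4 sets when the analysis runs, and 4.5.2 alone decides who is in the control.

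A second objection is that non-concurrent controls are already a disclosed choice. Patients randomized before a site opened also lack concurrent zilucoplan patients, and COV-01-001 accepts them too. That stands: a closing date removes one source of non-concurrency and leaves the other. The reason given, reducing imbalance, explains a wider pool. It does not explain why only this sub-protocol has no end date.

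A third is limited impact, and this also largely stands. COV-01-005 SAP sections 7.3 and 16 rule out efficacy inference. Master SAP section 17 also provides separate safety summaries for the sub-protocol's own placebo patients.

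A reader might be tempted to infer more than the documents support:
- **That late patients did enter the control.** No document shows a placebo patient randomized at a qualifying site after 07-Jun-2021.
- **That the open pool ties the zilucoplan analysis to the end of other enrolment.** That tie comes from the requirement in 4.4 for final lock of every contributing sub-protocol. COV-01-001 SAP 4.4 has the same requirement with a closed pool, and a closing date would not remove it.
- **That a few late patients would swamp the control.** The 7:1 ratio describes the Master SAP definition, which 4.5.2 replaces. The size of the redefined control is not given, so no such comparison can be made.

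**Conclusion.** The point holds as a defect in a stated selection rule. COV-01-005 SAP 4.5.2 has no closing date, and read literally it admits placebo patients randomized after zilucoplan enrolment ended. This departs from the Master Protocol, Master SAP 4.5 and the COV-01-001 rule without explanation.

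The size cannot be estimated. The number of affected patients is not reported and may be zero, in which case no result changes. If there are some, they affect only descriptive comparisons, within-arm intervals and the shared-control safety summaries.

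The conclusion rests on reading 4.5.2 as written and on 07-Jun-2021 being the last date on which a COV-01-005 patient could have been randomized. It does not rest on any claim that outcomes differed after that date. It is worth correcting before the final analysis, but it does not threaten an inferential result.

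**What to change.** In COV-01-005 SAP 4.5.2, limit the control to placebo patients randomized before enrolment into this sub-protocol was terminated (07-Jun-2021), matching COV-01-001 SAP 4.5.2. List the control redefinition in section 3.3, as COV-01-001 does. If an open pool was intended, say so, justify the difference from COV-01-001, and report how many controls were randomized after 07-Jun-2021.

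The cost is one phrase and one entry in the list of changes. The pooled control may be somewhat smaller, which works slightly against the aim of reducing the imbalance. Controls randomized before site opening remain, as in COV-01-001.
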